#### **3.3.2 Enrollment**

To enter a patient, the investigator or study team member will contact the assigned study coordinator at the respective study site. All eligibility requirements must be reviewed by the study coordinator or the Principal Investigator, and the eligibility checklist must be completed and signed by the Principal Investigator or designated Sub-PI prior to initiating registration to enter the patient on study. Once the eligibility checklist is signed, the patient will be enrolled in Velos. The research staff will then randomize the patient. The following information will be retained in the patient's study chart:

- 1) Completed and signed protocol-specific eligibility checklist;
- 2) All pages of the original signed informed consent forms (ICFs), including HIPAA Form B and photo consent form.
- 3) Relevant source documents such as: subject medical history and physical exam, admission or discharge notes, diagnostic reports, pathologic confirmation of diagnosis, and relevant subject-specific written communication.

##### **3.3.2.1 Cancellation Guidelines**

If a subject does not complete protocol therapy or no longer wishes to receive therapy, the subject may withdraw. [name] may also

withdraw patients if it is in their best interest. Subjects who are enrolled on study but not treated will be excluded from all analyses.

#### 3.3.2.2 Emergency Registration

None

#### 3.3.3. Randomization

Randomization of study subjects will be done in 3:1 ratio to the treatment arm and control arm. Due to the nature of study treatment, this is an unblinded study. A randomization list will be prepared by the SCCCBiostatistics and implemented by the research staff.

After each patient's study eligibility is confirmed and the informed consent is signed, the research staff will enter the required subject information into the CIERRA system in order to register the subject. The coordinator of the PI will receive the designated patient ID, study arm, randomization number, and randomization date. Coordinator will print the randomization confirmation form from the CIERRA system and place it in the subject's research chart and then notify the requesting member of the study team of the treatment assignment for the new randomized subject.

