## 4.0 TREATMENT PLAN

Subjects in the treatment arm will receive 3 treatments using the 595/1064 multiplex laser spaced by a four week interval (+/- 7 days), administered in an outpatient clinic setting. If a subject in the treatment arm has multiple BCCs satisfying inclusion criteria, all BCCs will be treated. The treatment settings for this laser will be as follows:

595 nm PDL at a fluence of 10 J/cm^2, a 10 ms pulse duration, and a 10 mm spot size, followed by 500 ms multiplex interpulse delay, followed by 1064 nm laser at a fluence of 40 J/cm^2, 10 ms pulse duration, and 10 mm spot size; the BCC lesion will be treated using 10% overlap with a single pass, along with 4 mm of normal skin. Dynamic cooling feature (cool air being blown onto treatment area) will be provided.

Subjects in the control arm will receive 3 regular study visits spaced 4 weeks (+/- 7 days) apart. If a subject in the control arm has multiple BCCs satisfying inclusion criteria, all BCCs will not be treated.

Four weeks (+/- 7 days) after the last (Day 84) both treatment and control patients will be assessed for final clinical appearance, measurement, and evaluation of the lesion by a dermatologist. Perpendicular diameters of the lesion will be measured with a ruler, as on initial evaluation, and surface area will be calculated. Residual tumor burden will be calculated based on change in surface area of the lesion.

Subjects will also undergo deep excisional biopsy encompassing the entire lesion to determine residual tumor cell presence. If histologic examination of the tissue reveals residual BCC, then the subject will receive standard of treatment.

A digital camera will be used to photograph the BCC immediately before, during and after treatment.

**Note:** If any clinical signs of progression are visible during this period (what we will consider greater than 10% growth), the subject in either treatment arm or control arm will be withdrawn from the study and undergo standard of care. Such a subject will be considered non-responder for the efficacy analysis.

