## 5.3 Post-treatment evaluation

Four weeks after the last of the 3 treatment sessions or follow-up visits (day 84 +/- 7 days) subjects will be asked about any side effects, reactions or adverse events that have occurred since the last visit. In the treatment arm, a dermatologist will then evaluate for any gross residual lesion as per protocol defined response criteria (see section 9.0) and a deep excisional biopsy encompassing entire region will be performed. Biopsy specimen will be evaluated for histopathologic clearance of tumor. If tumor cells are present, standard of care will be performed. In the control arm, biopsy specimen will be evaluated for histopathologic clearance of tumor and after gross evaluation and measurement of lesion by a dermatologist, standard of care will be performed.

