### 13.2 Sample Size Justification/Accrual Rate

The analysis set (evaluable subjects) consist of study-eligible subjects who either complete three treatments/three study visits and the biopsy visitor are withdrawn from the study due to showing evidence of PD during the study (non-responder). Subjects will be non-evaluable when they do not wish to continue in the study, are unable to continue in the study, or they cannot complete treatments or study visits for any reason other than PD. There will be 15 evaluable subjects in the treatment arm and 5 evaluable subjects in the control (non-treatment) arm. We expect that three to four subjects in both treatment arm and control arm will be non-evaluable. Therefore, the planned maximum number of enrolled subjects will be 28. The number of subjects is small due to the preliminary nature of the study, yet similar in size to previous studies (Konnikov et al 2011 and Shah et al 2009), which only used the 595 nm laser. Out of our 15 subjects in the treatment arm, we expect eleven or more subjects will respond to proposed treatment (either CR or PR). The table below shows significance (p-value) of hypothetical study findings assuming one BCC per subject. As shown in the second row, if one out of five subjects in the control arm shows either CR or PR and twelve or more out of fifteen subjects in the treatment arm show either CR or PR then test of comparing proportions of two arms is statistically significant (p-value < 0.05). If none in the control arm show either CR or PR and nine or more out of fifteen subjects in the treatment arm have either CR or PR, we also get a statistically significant difference indicating a better response rate in the treatment arm.

Number of subjects (CR or PR) among 15 subjects in the treatment arm vs. 5 in control arm	p-value*
11 (73.3%) vs. 1 (20%)	0.058
12 (80%) vs. 1 (20%)	0.031
9 (60%) vs 0 (0%)	0.030

\* one-sided Fisher's exact test (assuming every subject has one BCC)

One to two subjects will be accrued per week secondary to availability of the laser.

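### The plan specifies no masking of the Day 84 histology and ruler readings, although response turns on about half a millimetre per diameter of a 10 mm lesion

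*Combined protocol and SAP*

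**What the plan says.** Section 3.3.3 gives one reason for the open design: "Due to the nature of study treatment, this is an unblinded study". The Schema and Section 13.1 repeat the unblinded label.

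The Day 84 outcome rests on two readings.

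- **Ruler.** Section 4.0 says "Perpendicular diameters of the lesion will be measured with a ruler, as on initial evaluation". Section 9.1 turns the two diameters into an elliptical area. Section 5.3 assigns the clinical evaluation to a dermatologist and does not say whether that person also treats the subject. Under Section 5.2 the lesion is photographed and measured at every visit, so earlier values are on file.
- **Histology.** Section 5.3 says "Biopsy specimen will be evaluated for histopathologic clearance of tumor". It does not say who reads the specimen or what that reader is told.

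No section masks either reading to arm or keeps earlier measurements from the Day 84 examiner.

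Sections 2.1 and 13.1 make CR or PR the primary endpoint. In the Section 9.2 table, a lesion that has gone or is at most 90% of its baseline size is a response whatever the histology, and a larger lesion is SD or PD whatever the histology. The Section 9.2 text differs: it gives CR to a lesion that is still clinically present if histology is negative, with no size condition.

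**The concern.** A laser cannot easily be hidden from the subject or the operator. A specimen can be read without the arm on the requisition, and a diameter can be written down before the baseline value is looked up. The stated reason for an open study covers neither reading.

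This matters because the response threshold is close to what a ruler can resolve. An examiner who knows the arm and has the baseline in view knows which reading makes the subject a responder. Rounding in a favourable direction would then enter the arm comparison directly. That comparison informs the question in Section 13.1, whether the laser merits further study.

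**Working it through.** **Inputs.** Section 3.3.3: "Randomization of study subjects will be done in 3:1 ratio to the treatment arm and control arm". Section 13.2: "There will be 15 evaluable subjects in the treatment arm and 5 evaluable subjects in the control (non-treatment) arm". The test is labelled "one-sided Fisher's exact test (assuming every subject has one BCC", and 0.05 is the level used: "then test of comparing proportions of two arms is statistically significant (p-value < 0.05". Section 3.1.4 caps diameter at 15 mm. The lesion sizes of 6 and 10 mm below are assumptions.

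**1. The plan's own p-values.** With a treated and b control responders and t = a + b, the one-sided Fisher p is the sum over x ≥ a of C(15,x)·C(5,t−x)/C(20,t).

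- 11 vs 1: (1365×5 + 455)/125970 = 7280/125970 = 0.058
- 12 vs 1: (455×5 + 105)/77520 = 2380/77520 = 0.031
- 9 vs 0: 5005/167960 = 0.030

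All three match the Section 13.2 table.

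**2. The response threshold in millimetres.** In the area ratio π/4 cancels, leaving (d1′×d2′)/(d1×d2). Response needs a ratio of 0.90 or less. An equal fall in both diameters must be a fraction 1 − √0.90 = 0.051 of each. A fall in one diameter alone must be 0.10 of it.

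| Baseline diameter | Fall on each diameter | Fall on one diameter only |
|---|---|---|
| 6 mm | 0.31 mm | 0.6 mm |
| 10 mm | 0.51 mm | 1.0 mm |
| 15 mm | 0.77 mm | 1.5 mm |

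For example, 9×10/(10×10) = 0.90, which the table counts as response.

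**3. Effect of one treated subject reclassified from responder to non-responder.**

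- 12 vs 1 becomes 11 vs 1: p from 0.031 to 0.058; crosses 0.05.
- 9 vs 0 becomes 8 vs 0 (6435/125970): p from 0.030 to 0.051; crosses 0.05.
- 11 vs 0 (1365/167960) becomes 10 vs 0 (3003/184756): p from 0.008 to 0.016; does not cross.

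**4. Random error against directional error (illustration).** Step 3 alone does not separate bias from noise, since random ruler error can also move one subject. A simulation assumed no true change in size, diameters of 6 to 15 mm, a reading SD of 0.5 to 1.0 mm per diameter, and treated Day 84 readings shifted down on both diameters. None of these figures is in the documents. The probability of p < 0.05 was:

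- no shift: at most 0.007
- 0.25 mm: at most 0.045
- 0.5 mm: 0.009 to 0.243
- 1.0 mm: 0.21 to 0.80

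Under these assumptions random error rarely produces a false positive, while a consistent shift of 0.5 to 1 mm can.

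**5. What each reading can change.** Under the Section 9.2 table, histology separates CR from PR and cannot alter CR+PR. Under the Section 9.2 text, negative histology alone makes a visible lesion a CR and so a response. The conflict lies in the two table cells with negative histology and a lesion above 90% of baseline, which the plan marks as not expected.

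**The case against.** The strongest reply is that this is a pilot of 20 evaluable subjects with an openly declared design, that 0.05 illustrates the sample size and is not a stated go/no-go rule, and that the proposed steps only partly reach the primary endpoint. Much of this stands. The plan also says "we expect eleven or more subjects will respond to proposed treatment (either CR or PR"; with 11 treated responders and none in the control arm, one misreading does not matter at the 0.05 level.

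Four stronger readings are tempting, and the documents do not support them.

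- **That both readers know the arm.** For histology this would be inferred from the unblinded label plus silence. The documents support only that masking is not specified.
- **That locking the diameters first masks the ruler reading to arm.** It hides earlier values only. Section 4.2 says pigment change may take 3 to 6 months to fade, and Day 84 falls about four weeks after the third session. An examiner who attended earlier visits may also recall the baseline, which the progression rule in Sections 4.0 and 11.1 requires someone to consult.
- **That a control lesion read too small shows the same bias.** It would move 9/15 vs 0/5 to 9/15 vs 1/5 (28028/184756 = 0.152), but that favours the control arm, against the direction of concern.
- **That current staff can carry out a fuller scheme, such as an independent examiner.** Staffing is not described.

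Withholding all photographs would also be impractical: a cleared site must be found, and a subject may have several BCCs to match.

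The reply does not remove the core point. A pilot meant to judge whether the laser merits further study still depends on an even-handed reading of the endpoint.

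**Conclusion.** The point holds as an inexpensive improvement that should be made. The plan specifies no masking of the Day 84 readings, and its stated reason for being unblinded does not cover them. The main exposure is the ruler reading, because the 9.2 table makes CR+PR depend on about 0.5 mm per diameter at an assumed 10 mm, with a range of 0.3 to 0.8 mm over 6 to 15 mm. One reclassified treated subject crosses 0.05 in some of the plan's own scenarios and not in others.

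The Fisher figures assume one BCC per subject; Section 13.3.2 uses a different test otherwise. The simulated probabilities rest on assumed reading error and shift. A reader might infer that the trial's results will be biased. The documents do not show that; they show that the endpoint is sensitive and has no stated protection.

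**What to change.** Add to Sections 5.3 and 9.1:

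1. The study arm is withheld from the Day 84 pathology requisition and specimen label until the report is signed. This protects the CR rate and histological clearance. It also protects CR+PR if the Section 9.2 text governs over the table. The text and table must be reconciled in any case.
2. The Day 84 diameters are recorded and locked before the baseline, Day 28 and Day 56 measurements are opened. Photographs are used beforehand only as needed to locate or match the lesion.
3. A statement that the clinical examination remains open to knowledge of arm, through residual pigment change or recall of earlier visits, so that step 2 reduces bias without removing it.

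The cost is a small change in labelling and form order. No extra assessor or procedure is proposed, and the sample size, test and stated p-values do not change.

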## 4.0 TREATMENT PLAN

Subjects in the treatment arm will receive 3 treatments using the 595/1064 multiplex laser spaced by a four week interval (+/- 7 days), administered in an outpatient clinic setting. If a subject in the treatment arm has multiple BCCs satisfying inclusion criteria, all BCCs will be treated. The treatment settings for this laser will be as follows:

595 nm PDL at a fluence of 10 J/cm^2, a 10 ms pulse duration, and a 10 mm spot size, followed by 500 ms multiplex interpulse delay, followed by 1064 nm laser at a fluence of 40 J/cm^2, 10 ms pulse duration, and 10 mm spot size; the BCC lesion will be treated using 10% overlap with a single pass, along with 4 mm of normal skin. Dynamic cooling feature (cool air being blown onto treatment area) will be provided.

Subjects in the control arm will receive 3 regular study visits spaced 4 weeks (+/- 7 days) apart. If a subject in the control arm has multiple BCCs satisfying inclusion criteria, all BCCs will not be treated.

Four weeks (+/- 7 days) after the last (Day 84) both treatment and control patients will be assessed for final clinical appearance, measurement, and evaluation of the lesion by a dermatologist. Perpendicular diameters of the lesion will be measured with a ruler, as on initial evaluation, and surface area will be calculated. Residual tumor burden will be calculated based on change in surface area of the lesion.

Subjects will also undergo deep excisional biopsy encompassing the entire lesion to determine residual tumor cell presence. If histologic examination of the tissue reveals residual BCC, then the subject will receive standard of treatment.

A digital camera will be used to photograph the BCC immediately before, during and after treatment.

**Note:** If any clinical signs of progression are visible during this period (what we will consider greater than 10% growth), the subject in either treatment arm or control arm will be withdrawn from the study and undergo standard of care. Such a subject will be considered non-responder for the efficacy analysis.

#### **4.1 Agent Administration**

**Subjects in the treatment arm** will receive 3 treatments using the 595/1064 multiplex laser spaced by a four-week interval (+/- 7 days), administered in an outpatient clinic setting. Prior to treatment, the area will be cleaned and dried. Application of a topical anesthetic will not be necessary but is available upon request.

The treatment settings for each laser session will be as follows:

595 nm PDL at a fluence of 10 J/cm^2, a 10 ms pulse duration, and a 10 mm spot size. After a 500 msec interpulse delay, a second pulse with 1064 nm laser at a fluence of 40 J/cm^2, 10 ms pulse duration, and 10 mm spot size will be administered; the BCC lesion will be treated using 10% overlap with a single pass, along with 4 mm of normal skin. Dynamic cooling feature (cool air) will be provided.

**Subjects in the control arm** will not receive any treatment; however they will receive 3 regular study visits spaced 4 weeks (+/- 7 days).

## 4.2 Supportive Care Guidelines

The 595/1064 nm multiplex laser has a cooling feature (Smart cool 6-air cooling system) available for patient comfort during laser sessions. If the subject is concerned about being uncomfortable during the laser treatment session, an additional topical anesthetic may be applied before each treatment.

After treatment, should the subject experience any expected or unexpected adverse side effects, supportive care will be offered. These include:

- Skin pain: The subject may experience discomfort during and immediately after laser treatment. This typically resolves within 24-48 hours. Administration of topical and/or oral pain care will be determined on a case-by-case basis.
- Skin ulceration or bullous dermatitis: The laser may cause slight cutaneous disruption that can take several days to heal. The disruption may lead to mild swelling or crusting that may remain photosensitive for 2-12 weeks following treatment. Subjects will be informed of the potential risk and will be advised to wear sunscreen before and after treatment. Any blistering or crusting that occurs after therapy will be treated with washing the site with soap and water followed by topical application of Vaseline and tefla/gauze dressing.
- Skin hyperpigmentation or hypopigmentation: The site of laser application may heal with some post-treatment pigment changes. This adverse effect is more common in darker-skinned individuals, who will be excluded from this study for this reason. It may also occur following sun exposure. Subjects will be urged to wear sunscreen before and after treatment. Pigment alterations that do arise will generally fade in 3-6 months
- Scarring: A small chance of scarring exists. Rarely, hypertrophic scars or keloids may form in response to laser treatment. If this unusual complication should occur, intralesional triamcinolone acetonide in concentration of 10-40mg/mL at 4-6week intervals will be used to diminish the appearance.
- Skin infections: Cutaneous infection can occur with the use of laser therapy, although rare, and would require antibiotic treatment. In such circumstances, antibiotics will be given according to standard of treatment for cutaneous infection.
- Erythema/Purpura: Immediately post-laser, the treated skin is expected to become red and splotchy. This is followed by a purpuric response, where the affected area becomes purple or violaceous. This response

is expected and may worsen in the 24-48 hours immediately post-treatment and may last as long as 10 days. Reassurance will be given to subjects.

#### 4.2.1 Concurrent Medication (if applicable)

The following are part of eligibility criteria and as such we prohibit patients from starting any of the following medications:

- Medications that increase sensitivity to light
- Medications that alter wound healing
- Isotretinoin
- Gold therapy

Should the subject be required, or desire to, begin treatment with any of the above medications, they will either be removed from the study or considered inevaluable for response.

Resources for examples of these agents may be seen in appendix VI.

### 4.3 Duration of Therapy

The laser therapy will take place in three sessions with 4-week intervals between sessions. A final biopsy will occur four weeks later after the last treatment with one-week follow-up for biopsy wound care and check-up. Thus, study involvement will require approximately 13 weeks of commitment.

## 5.0 CLINICAL AND LABORATORY EVALUATIONS

### 5.1 Baseline/pretreatment evaluation

Prior to involvement in the study

Prior to consideration of being a possible participant in the study, patients will receive a diagnostic biopsy as is the standard practice for evaluation of lesions that are suspicious for BCC.

Patients that present to [name] clinic for follow-up of their biopsy who have biopsy proven superficial or nodular basal cell carcinoma will be approached to participate in the study. We will identify patients who have biopsy proven superficial or nodular basal cell carcinoma on the trunk or extremities that is less than 1.5 cm in size via medical records (partial waiver

of authorization approval). If patients have more than one BCC that satisfy inclusion criteria, they will also be treated.

After signing informed consent, patients will be fully evaluated for eligibility criteria. Patients will be randomly assigned in either a control arm or treatment arm. Patients will be advised that if placed in control arm, there is an extremely low risk of serious progression during the short time needed for the study and that should any clinical signs of progression be seen, they would be withdrawn from the study and receive immediate surgical excision.

Patients will be entered into Velos system and completed HIPAA forms will be sent to HIPAA privacy office as per University of Miami policy.

## 5.2 Evaluations during treatment

After enrollment (day 0), subjects in both control and treatment arms will receive standard baseline photographs of their lesion. Subjects in the treatment arm will receive their first laser treatment. Lesions will be assessed by [name] and documented, as well as monitoring for adverse effects and reviewing "prohibited" medications.

Days 28 and 56 (+/- 7 days) correspond to treatment sessions #2 and #3 for the treatment arm, and study visits #2 and #3 for the control arm. At these visits, patients will be asked of any side effects, reactions, or adverse events that occurred since the last visit as well as any other concerns. These will all be documented. If any serious adverse events have occurred, they will be reported to the IRB as per University of Miami policy.

Photographs and measurements of the lesion will be taken at each study visit. Subjects in the treatment arm will then receive laser treatment and patients in the control arm will receive a standard study visit.

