### APPENDIX I: STUDY CALENDAR

Procedure	Screening	Randomization 	Day 0	Day28 (+/- 7 days)	Day 56 (+/- 7 days)	Day 84 (+/- 7 days)	Day 91 (+/- 7 days)/ Follow up visit
Written Informed Consent	X						
HIPAA	X						
Photo consent	X						
Eligibility checklist 	X						
Velos	X						
Randomization		X					
Pt and lesion characteristics 			X	X	X	X	

Treatment #1 			X				
Treatment #2 				X			
Treatment #3 					X		
Photographs are taken			X	X	X	X	
Monitoring of adverse events and concomitant medication			X	X	X	X	X
Dermatologic eval for clearance						X	
Excisional biopsy						X	

Within 3 months of initial diagnostic biopsy and within 1 week of enrollment (+ 3 days)

 Source document titled "Enrollment"

 Source document titled "Patient information"

 Or regular study visit for control arm

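### In an open-label trial, the first scheduled lesion measurement comes after the arm is known, and no reading made before allocation is named as the baseline for response

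*Combined protocol and SAP*

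**What the plan says.** **Order of events.** Section 3.3.2 has the eligibility checklist signed and the patient enrolled in Velos, and then "The research staff will then randomize the patient". Section 3.3.3 states "Due to the nature of study treatment, this is an unblinded study", and has the coordinator "notify the requesting member of the study team of the treatment assignment for the new randomized subject".

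**Baseline record.** Section 5.2 reads "After enrollment (day 0), subjects in both control and treatment arms will receive standard baseline photographs of their lesion", and adds that photographs and measurements are taken at every study visit. In Appendix I the screening column holds the consents, HIPAA, the eligibility checklist and Velos. Randomization is the next column. The row "Pt and lesion characteristics" and the photograph row are first marked at Day 0, the visit of the first laser session. Section 5.1, the baseline section, describes no measurement or photograph.

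**How size is used.** Section 4.0 says "Perpendicular diameters of the lesion will be measured with a ruler, as on initial evaluation, and surface area will be calculated". Section 9.1 computes the area of an ellipse from the two diameters. The Section 9.2 table sets the limits for response and progression at 90% and 110% of baseline size, and Section 2.1 makes CR or PR the primary endpoint.

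**The concern.** Randomisation protects a baseline value only if that value is fixed before allocation is known. Here the scheduled baseline reading is made with a ruler, on a lesion whose border is a matter of judgement, after the team has learned whether the subject will receive the laser. The plan describes no masked reader, second reader or reference measurement made before allocation.

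The reading matters because it is a denominator. A slightly generous border in the laser arm, or a tight one in controls, would produce partial responses with no change in the lesion. It would also move the 10% progression limit further from reach in the laser arm. Masking the Day 84 assessment alone would not repair a biased denominator.

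**Working it through.** **1. The plan's own figures.** Section 13.2 gives one-sided Fisher p-values for 15 vs 5 subjects. From the hypergeometric distribution:

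- 11 vs 1: [C(15,11)·C(5,1) + C(15,12)] / C(20,12) = (6825 + 455)/125970 = 0.0578 (stated 0.058)
- 12 vs 1: [C(15,12)·C(5,1) + C(15,13)] / C(20,13) = (2275 + 105)/77520 = 0.0307 (stated 0.031)
- 9 vs 0: C(15,9)/C(20,9) = 5005/167960 = 0.0298 (stated 0.030)

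All three reproduce.

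**2. Which outcomes use the baseline.** A lesion no longer visible at Day 84 is CR or PR whatever its baseline. A visible lesion with positive histology is PR at or below 90% of baseline and SD or PD above it, so there size alone decides response. For a visible lesion with negative histology, the Section 9.2 text gives CR without reference to size, while the table gives CR only at or below 90% and SD or PD above. Text and table must be reconciled.

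**3. Over-reading needed.** I take size in Section 9.2 to mean the Section 9.1 surface area, SA = π·r1·r2, which is proportional to d1·d2. If the lesion does not change and Day 84 is read correctly, PR requires true area / recorded baseline area ≤ 0.90.

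- Both diameters over-read by a fraction e: 1/(1+e)² ≤ 0.90, so e ≥ 1/√0.90 − 1 = 5.4%.
- One diameter over-read: 1/(1+e) ≤ 0.90, so e ≥ 1/0.90 − 1 = 11.1%.

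| True diameter | Both axes | One axis |
|---|---|---|
| 6 mm | 0.32 mm | 0.67 mm |
| 8 mm | 0.43 mm | 0.89 mm |
| 10 mm | 0.54 mm | 1.11 mm |

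**4. Upper limit.** Section 3.1.4 caps the diameter at 15 mm. If Day 0 readings are held to that cap, a round lesion can be converted only up to 15 × √0.90 = 14.2 mm.

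**5. Progression limit.** With an over-read just large enough to create a PR, the recorded baseline is 1/0.90 = 1.111 times the true area. The 110% limit is then reached only at 1.10 × 1.111 = 1.222 times the true area, a growth of 22%.

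**6. Effect on the test.** One extra false PR in the laser arm moves 11 vs 1 (p = 0.058) to 12 vs 1 (p = 0.031). It likewise moves 8 vs 0, where p = C(15,8)/C(20,8) = 6435/125970 = 0.051, to 9 vs 0 (p = 0.030).

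**7. Illustration on assumed inputs.** The documents give neither the lesion size distribution nor the ruler error. Assume 10 mm lesions, a reading SD of 0.5 mm per diameter, no true change, one lesion per subject, an unbiased Day 84 reading, and over-reading of both diameters in the laser arm only. From 400,000 simulated lesions per setting and the exact Fisher rejection region:

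| Over-read, laser arm | False-PR rate, laser arm | Chance of p < 0.05 |
|---|---|---|
| none | 14.7% | under 0.1% |
| 0.5 mm | 46.9% | about 10% |
| 1 mm | 81.5% | about 75% |

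With SD from 0.25 to 1.0 mm and lesions of 6 to 14 mm, the last column runs from about 0% to 72% for 0.5 mm and from 19% to over 99% for 1 mm. The 15 mm cap was not imposed, so the 14 mm settings overstate the effect. With no over-reading, the false-positive chance is at most 0.7%.

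**The case against.** The strongest reply is that a size is already known before allocation. Section 5.1 has patients fully evaluated for eligibility after consent, and mentions random assignment only afterwards. Eligibility includes diameter, and Section 4.0 refers back to an initial evaluation. The calendar ties the lesion row to a source document that is not reproduced, so one cannot confirm that the two diameters are first written down there. Section 5.2 also loosely equates Day 0 with enrolment. This stands in part: an earlier reading may exist. But eligibility needs only a diameter of 1.5 cm or less, the initial evaluation is undated, and no section makes an earlier value the baseline. Even if everything happens on one day, nothing places the measurement before release of the arm.

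A second reply is that the Section 5.2 sentence concerns photographs, and knowing the arm does not enlarge a lesion in a photograph. That is right. The Day 0 measurement rests on the calendar and on the statement that measurements are taken at each visit. A photograph taken before treatment could be re-read by someone unaware of the arm, but the plan does not provide for this.

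Third, over-reading shared by both arms raises false PRs in both and does not favour the laser. That also stands: the harm requires an error that depends on the arm, and the documents give neither its size nor its direction.

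Last, this is a pilot with 20 evaluable subjects and no stated power, meant to inform a larger trial. That lowers the severity but does not remove the point.

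**Conclusion.** The point holds in a limited form and should be fixed. The first scheduled lesion measurement follows open allocation, and no pre-allocation reading is named as the baseline. For visible lesions with positive histology, response then turns on a denominator that can be moved across its limit by 5.4% on both diameters or 11.1% on one. In a 15 vs 5 comparison, one such lesion can decide which side of 0.05 the result falls.

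The conclusion assumes that size in Section 9.2 means surface area. Any bias between the arms further requires arm-dependent reading error, which is possible under the plan but not shown. The false-positive rates above are illustrations, not estimates.

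A reader might infer three stronger things that the documents do not support:

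- **Every response category depends on the baseline.** Complete clinical clearance does not, nor does the text's CR for a visible lesion with negative histology.
- **A 1 mm over-read turns every unchanged eligible lesion into a PR.** For a 15 mm lesion this needs a recorded diameter of 16 mm, outside the eligibility limit. With readings held to 15 mm, round lesions above about 14.2 mm cannot be converted.
- **An earlier baseline would remove the measurement bias.** It removes only the denominator part, because the Day 84 reading is made in the same open-label setting.

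**What to change.** In Appendix I, move the recording of d1 and d2 and the baseline photograph, for each target BCC, to a point after consent and before randomisation, and date them. Reword Sections 5.1 and 5.2 to match. Require both diameters to be entered at CIERRA registration before the arm is released. State in Section 9 that these values are the baseline for response and for percentage change, and replace the undated reference in Section 4.0 with a reference to them. In the same amendment, reconcile the text and table of Section 9.2 for a visible lesion with negative histology.

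The cost is a calendar and wording amendment. Sample size, test and treatment do not change, and subjects are already seen in person for consent. The downside is that the baseline may precede Day 0 by some days, equally in both arms. Where feasible, having someone unaware of the arm read the baseline and Day 84 images would address the part of the bias that this change leaves open.
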